Radiation is essential component of breast conserving therapy. The use of RT improved recurrence free, breast cancer specific survival and overall survival in both patients with negative and positive axillary lymph nodes in the most recent metaanalysis of Early Breast Cancer Trialists Collaborative Group (EBCTCG)⁵ which included trials begun before 2000. It included data from 42080 patients with breast cancer treated in 78 clinical trials that investigated locoregional treatments between 1952 and 1995. Among those patients were 7311 patients treated in 10 trials comparing radiation vs no radiation after breast conserving surgery and 9933 patients treated in 25 trials comparing radiation vs no radiation after modified radical mastectomy. In the trials that investigated radiation as a component of breast conserving therapy, radiation was shown to reduce the risk of local recurrence by two thirds and to improve the absolute 15 year overall survival rate by 6% (41% versus 35%). Similarly for patients with positive lymph nodes treated with modified radical mastectomy, radiation reduced the risk of locoregional recurrence rate by 21% at 15 years (29% versus 8%), which was associated with a 5% decrease in the 15 year breast cancer mortality rate (60% versus 55%). A more recent update of the analyses continues to demonstrate locoregional and survival advantages for radiation therapy

Even if surgical margins are negative after BCS, 30-40% risk of microscopic tumor cells in tumor bed. Most recurrences (65-80%) are located in vicinity of tumor bed as shown in EORTC⁶ trial and NSABP-06 trial. It is therefore important to ensure the tumor bed lies well inside the treatment volume encompassed by tangential fields to whole breast and subsequent tumor bed boost. There is also a pathological basis for giving boost to tumor bed-residual tumor foci have been reported in 1-2 cm in around 20-25% patients/histopathological specimens.

The EORTC 22881-10882⁷ trial studied the effect of addition of a boost dose on the primary tumor bed after lumpectomy in breast conserving treatment for breast cancer. It included 5318 patients who received whole breast irradiation after lumpectomy and then randomised to boost of 16 Gy to tumor bed or no boost. The median follow up was 10.8 years. It was found that 47% of local recurrences were in primary tumor bed, 10% in scar, 29% outside original tumor area and 13% were diffuse. At 10 years, the cumulative incidence of local recurrence was 10.2% versus 6.2% for the 0 Gy and the 16 Gy boost groups (p< 0.0001).

Regarding surgical techniques for BCS, two main methods can be distinguished: open cavity and closed cavity technique. In the former only the superficial part of the cavity is closed allowing the formation of seroma. During closed cavity technique a full thickness closure is performed by suturing the deep and superficial layers of the surrounding breast tissue. In this case seroma does not develop and the target volume definition can be much more difficult.

Oncoplastic surgery represents a special form of closed cavity breast conservation tumorsurgery. The advantage of oncoplastic surgery is the combination of tumour excision and immediate reconstructive surgery. Because of the excellent cosmetic results oncoplastic surgery has become more frequent in the past years. However adjuvant radiotherapy procedures have to face the possibility of breast tissue displacements at risk of residual tumor cells, influencing the post operative target definition for partial breast irradiation

The tumor beds of medially and laterally located tumors are particularly prone to underdosage if surface landmarks are used as fiducial points for whole breast RT planning. It is therefore very important to localise the tumor bed even for whole breast RT planning. Clinical planning of tumor bed boost volume based on preoperative imaging, surgical note and breast scar position is very unreliable. Increasingly the breast scar is placed often some distance from the tumor for wire guided localisation biopsy or better cosmetic outcome. In addition the practice of oncoplastic surgery where breast tissue is repositioned following wide excision to minimise the surgical deficit is becoming standard of care. In this situation the preoperative imaging bears very little final relation to tumor bed.

Computed tomography and ultrasonography can use the seroma as a surrogate for tumor bed position, but there are limitations. First, the seroma is only clearly defined in only about quarter of patients. Second the seroma underestimates the tumor bed defined by implanted clips.

Uncertainty in localising the tumor bed in medial or lateral tumors can be overcome by increasing the posterior field borders of whole breast tangents, but only at expense of increased morbidity of ribcage and lung, and potential mortality in women with left sided tumors. The heart is the most sensitive organ, a few Gy being associated with risk of heart disease and every effort needs to be made to exclude the organ from treatment volume. When localising the tumor bed boost, increasing the clinical target volume is a crude way of avoiding geographical miss. This is particularly important in the era of oncoplastic surgery when the tumor bed may be well away from its primary location.

Accurate delineation of the target volume is of utmost importance while delivering tumour bed boost with external beam radiotherapy. Different institutions use different methods for delineation of the tumour bed.

Clinical history and patients' recollection of tumour position, clinical photographs, tattoos, surgical scar, mammography, surgical clips, ultrasonography, Computerized tomography

(CT) scan and Magnetic resonance imaging (MRI) are the commonly utilized techniques. Many a times, a combination of one or more of these techniques is considered while delineating the tumour bed boost.

Amongst all the randomised trials assessing role of radiotherapy boost, surgical clips were used in all patients for assessing boost volume only in the Budapest trial⁸. In other studies, the boost volumes were usually defined on clinical and surgical details. It was hypothesized that increasing differences between local failure rates in whole breast radiotherapy (WBRT) arm versus WBRT+boost arm in Lyon trial (4.5% vs. 3.6%), EORTC trial (10.2% vs. 6.2%) and Budapest trial (15.5% vs. 6.7%) [may well have been due to the different techniques of tumour bed delineation as the difference in boost doses between all these trials were not significantly different. Hence an accurate delineation of tumour bed is important as it may translate into improved local control rates.

Tumor bed localisation and open or closed cavity BCS:With superficial closure, only the superficial aspect of the cavity is closed, allowing the formation of a seroma to prevent deformation of the breast. A full-thickness closure consists of repositioning of the surrounding breast tissue and suturing the deep and superficial layers, preventing the development of significant seroma. There is a paucity of data on the influence of surgical closure techniques on EB treatment planning. It can be hypothesized that superficial closure may lead to a better-delineated cavity as a well-visualized seroma has been shown to decrease interobserver variations nevertheless, it may also lead to a larger treatment volume and greater late toxicity effects. However, with full-thickness closure, the surgical clips may be displaced with the approximation of the surrounding breast tissue and not correlate with the true extend of the cavity. In a recently published single institutional experience, Shaikh et al.⁹ did not find statistically significant difference in mean cavity visualization scoring (CVS) (Smitt et al¹⁰, 1 = no visible cavity, 2–4 = heterogeneous cavity with indistinct, distinct, or clearly defined margins, 5 = homogenous cavity with clearly defined margins) or normal tissue dosimetric endpoints between 29 patients who underwent superficial closure and sixteen patients who underwent full-thickness closure. A higher percentage of patients who underwent superficial closure had CVS scores >2 (79% vs. 63%). The small patient numbers in each cohort and its retrospective nature are the limitations of the study.

Oncoplastic BCS techniques with parenchymal rearrangement present new challenges to the localisation of the tumour bed and therefore delivery of local boost radiotherapy. Although use of whole-breast radiation therapy (RT) is straightforward, difficulties in localization of the tumor bed for the local RT boost have not been investigated.

Pezner et al¹¹ carried out a retrospective review of 25 patients who received RT after breast conservation surgery with oncoplastic reconstruction. It was found that among 11 patients with a minimum of 4 surgical clips placed at tumor resection, 8 (73%) had the final tumor bed extend beyond the original breast quadrant or be completely relocated into a different

region. In 3 (27%) cases, the clinical treatment volume was 2 to 3 separated regions within the breast.

Thus, in breast cancer patients who have undergone oncoplastic surgery, the tumor bed is frequently more extensive and possibly more relocated compared to original presentation. Placement of surgical clips after tumor resection and before oncoplastic reconstruction may be the most accurate method to localize the RT local boost field^{12, 13}.

Techniques of Radiotherapy boost delivery-Variou techniques of tumor bed boost delivery have been extensively studied and their efficacy compared retrospectively and prospectively. The various techniques are electrons, photons(less commonly used due to higher penetration and increased doses to critical underlying structures) and interstitial brachytherapy (i.e. interstitial placement of needles into tumor bed either intraoperatively or postoperatively)

With most of the centres now having linear accelerators, coronal en face electron beams have now become standard practice in most institutions. Minimal dose to underlying normal structures, i.e. lung and breast to the maximum, varying energy of electrons, feasibility of defining field on skin, an outpatient procedure with minimal patient discomfort make it a favourable option for both the patient as well as treating radiation oncologist. Most commonly used energies are 9-12 MeV. However, the boost fields defined on the basis of clinical details have been found to be erroneous in several studies. Hence, the dimensions as well as depth for tumour bed boost should be determined either by fluoroscopy or CT combined with surgical clips, or an ultrasound. The most common prescription isodose for electron boost delivery is 90-95% isodose. But, in an organ such as breast with multiple edges and curvatures in different axes, the prescription isodose may not cover the whole target volume uniformly. This problem is commonly seen when tumours are located at areas where there is a sudden change in the depths like inframammary and axillary folds. The depths of soft tissue vary greatly in these areas and uniform energy electron beam may either underdose the tumour bed, or deliver higher dose to underlying normal structures. The electrons have limited role in patients with large breasts, tumours situated at a depth i.e. closer to heart (on left) and lungs and in folds. CT based planning in three dimensions may help to determine the dose distributions accurately and help in choosing the optimal energy.

The margins to be given to tumour bed for defining boost field have also been discussed. Harrington et al¹⁴ have shown that a boost field marked on the basis of clinical data and background with a margin of 2 cm all around covers radiological field with same margin in only 1/3rd (33%) of patients. Although Vicini et al. showed that a margin of 1 cm around the tumour covers microscopic disease adequately, in EORTC trial margins of 1.5 cm were given for microscopically completely excised tumours. Overall, a margin of 1.5-2 cm to the tumour bed has been reported to cover all subclinical disease in patients with clear microscopic margins.

Some institutions have practised tumour bed boost by 4-6 MV photons. The practice of delivering boost by photons has declined after widespread availability of electrons due to

higher penetration and increased doses to underlying critical structures. Photons can be used in patients with small tumour bed as late term sequelae of electrons such as telangiectasia may not be acceptable to some patients treated with electrons.

Aims and Objectives: Primary objective- To evaluate dosimetric outcomes in tumor bed boost irradiation in patients undergoing breast conservative surgery using three different surgical techniques

Secondary objective-Evaluation of cosmesis in patients prior to radiotherapy, at the time of completion of radiotherapy and 6 months post completion of radiotherapy

Material and methods-

Patients will be screened for the study at the time of radiotherapy simulation for External beam radiotherapy

The sample size has not been calculated as this is a pilot study. Twenty patients will be accrued for the purpose of this study. The patients will be divided into three groups:

Group A- Patients who underwent open cavity BCS

Group B- Patients who underwent closed cavity BCS

Group C- Patients who underwent oncoplasty

Inclusion Criteria- All patients undergoing Breast Conservative Surgery (Open Cavity/Closed Cavity) or Oncoplasty will be eligible for this study.

Exclusion Criteria-1. Patients undergoing Neoadjuvant chemotherapy will not be eligible for the purpose of this study.

2. All patients undergoing Modified Radical Mastectomy will not be eligible for the purpose of this study

Informed consent will be taken for all patients at the time of Radiotherapy simulation. All patients will first receive external beam Radiotherapy to the whole breast to a dose of 40Gy/15#/3weeks. The patients will then be planned for boost radiation to the tumor bed to a dose of 12.5 Gy/5#.

The combination of surgical clips with a treatment planning CT scan for the lumpectomy site for electron boost and to determine the appropriate energy will be used for tumour bed boost delineation

For the boost planning CT scan a small thermocol wedge will be used, with a pillow under the shoulder to make the surface as flat as possible.

The pT size in HPR of lumpectomy plus a margin of 2 cm in all directions is the approximate size of the boost field. The margins of this field are marked on the skin with the centre of scar as the center of the field and copper wire is placed on the markings.

5 mm slice thickness CT scan will be taken in the treatment position. After the scan acquisition the data will be transferred to the Varian Eclipse treatment planning system.

The post-operative cavity depicted on the CT images will be contoured section by section. All available images will be assigned a cavity visualisation score⁹ (CVS) as per the British Columbia Cancer Agency Cavity visualisation score 0-No visible seroma, 1-scar/shadow, 2-seroma identifiable but with significant (>30%) uncertainties, 3-seroma identifiable with minor (<30%) uncertainties, 4- seroma easily identifiable, generally homogenous with some blurring of margin, 5-seroma clearly identifiable, homogenous with sharp boundaries. The mean cavity visualisation score will be determined for each group of patients.

The CTV will be generated by using a 15 mm uniform expansion from the lumpectomy cavity but limited by skin and chest wall. The CTV will be extended by an additional 10 mm uniform expansion to generate the PTV

Treatment plans for tumor bed boost irradiation will be made using both electrons and photons with 3DCRT technique for each patient and comparison will be made for various dosimetric variables. The photon beam plan will only be generated for purposes of dosimetric study and will not be used for treatment of the patients

The following dosimetric variables will be determined for each patient -seroma cavity volume (ccs). PTV volume (ccs). In addition the ratio between the PTV volumes to the whole breast volume will be determined. The Radiation Conformity Index (RCI) will be determined for both set of plans. It was first defined by Knoos et al and a revised definition appeared in ICRU 62 It is the ratio of volume of the PTV to the volume that receives 95% prescribed dose or higher ($RCI = V_{PTV} / V_{95\%}$). The Dose Homogeneity Index (DHI) will be determined for both set of plans (DHI). It is ratio of dose received by 95% of PTV volume to the dose received by 5% of PTV volume ($DHI = D_{\geq 95\%(\text{within PTV})} / D_{\geq 5\%(\text{within PTV})}$). The dose received by several normal structures will be determined for both set of plans-normal ipsilateral breast tissue (Whole breast volume- PTV volume), contralateral breast, ipsilateral lung, contralateral lung and heart

The borders of the portal will be modified based on the position of the lumpectomy cavity/seroma of the scan and marked on the patient. The boost irradiation for all patients will be done using electrons. The energy of electrons required will be decided from the depth of the lumpectomy cavity.

In addition the cosmesis will be determined for all the patients prior to starting radiotherapy, at the time of conclusion of radiotherapy and 6 months post completion of radiotherapy. This will be done by using the criteria suggested by Harris et al

1. Excellent: the treated breast almost identical to the untreated one.
2. Good: the treated breast slightly different from the untreated breast.
3. Fair: obvious difference between the two sides without major distortion.
4. Poor: the treated breast is seriously distorted.

Statistical analysis shall be performed with the Statistical Package for Social Sciences (SPSS, Chicago, IL) software package, version 21.0, for Windows A two-tailed PValue less than 0.05 will be considered as statistical significance in this study. Descriptive statistics, including frequency distributions, means \pm SD, and 95% confidence intervals, to be calculated for demographic and treatment variables. The statistical analysis will be carried out using the One way ANOVA or Krsukal Wallis test and categorical comparison will be done using Chi Square test.

References:

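### The cavity visualisation score is a reader's judgement summarised by surgical technique, but the plan neither names the scorer nor withholds the technique; a coded re-read of the 20 scans would reduce the risk of bias

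*Combined protocol and SAP*

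**What the plan says.** Material and methods has the post-operative cavity contoured slice by slice on the boost-planning CT. The next sentence introduces the score: "All available images will be assigned a cavity visualisation score". The scale runs from 0 to 5, and its middle grades are worded "2-seroma identifiable but with significant (>30%) uncertainties, 3-seroma identifiable with minor (<30%) uncertainties". No rule is given for measuring the 30%.

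The between-group use is stated: "The mean cavity visualisation score will be determined for each group of patients". The groups are open cavity, closed cavity and oncoplasty, 20 patients in all, with no group sizes fixed. The statistical paragraph is general: "The statistical analysis will be carried out using the One way ANOVA or Krsukal Wallis test", with "A two-tailed PValue less than 0.05 will be considered as statistical significance in this study". It does not assign a test to the cavity score by name.

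The introduction states a direction. On superficial closure it says: "It can be hypothesized that superficial closure may lead to a better-delineated cavity". Its account of surgical techniques says that seroma does not form after closed-cavity surgery. It also cites a retrospective series in which 79% against 63% scored above 2, and reports that the same series found no statistically significant difference in mean score.

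The available text does not say who assigns the score, how many readers there are, or whether scans are coded. The start of the document was not available for review.

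**The concern.** Three features together create the risk. The grade is subjective, it is summarised by surgical technique, and the protocol says which technique may look better. A scorer who has just contoured the cavity using clips and surgical details would probably know the technique. When a scan lies between two grades, that knowledge can tip the choice in the expected direction.

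What is at stake is whether a difference in mean score between groups, if one appears, can be read as a difference in cavity visibility and not partly as the reader's expectation. The protocol itself links a well-seen seroma to smaller differences between observers, so it accepts that readings depend on the reader.

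**Working it through.** The plan states no power or bias figure to reproduce, and it says that the sample size was not calculated. The check has three parts.

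**1. The text set side by side**

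- Judgement-based: yes. Grades turn on perceived uncertainty, blurring and sharpness (Material and methods).
- Summarised by technique: yes, as a mean per group (Material and methods).
- Direction stated: yes, as a hypothesis for superficial closure and more firmly for closed cavity (introduction).
- Scorer named or technique withheld: neither, in the available text.
- Treatment dependent on the score: no. CTV and PTV are expansions of the contoured cavity, the portal follows the cavity's position, and electron energy follows its depth. A separate later reading would change nothing for the patient.

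**2. Is the expected direction established?**

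The cited series had 29 superficial and 16 full-thickness closures. The counts that match the percentages are 23/29 = 79.3% and 10/16 = 62.5%. Fisher's exact test gives p = 0.30 and the uncorrected chi-square test p = 0.22. The direction is plausible but not shown, which agrees with the series' non-significant mean score. That series used a 1-5 scale and this study uses 0-5, so the percentages do not carry over.

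**3. How much could scorer bias matter?**

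The documents give no mean, SD or group sizes for the score. Assumptions: a split of 7/7/6, true mean 2.5 in every group, SD 0.8 to 1.3, scores rounded and limited to 0-5, and a test at two-sided 0.05. There is no true difference, so every significant result is false. Ranges are over the assumed SDs.

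| Scoring of the open-cavity group | ANOVA | Kruskal-Wallis |
|---|---|---|
| No bias | 4.8-5.5% | 4.3-4.4% |
| One patient regraded from 2 to 3 | about 6% | 5-6% |
| All patients 0.5 point too high | 9.5-16.4% | 8.3-14.2% |
| All patients 1 point too high | 25-54% | 23-50% |

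In the two bottom rows the larger inflation belongs to the smaller SD. One regraded patient moves a group mean by 1/7 = 0.14 to 1/6 = 0.17 points. A single changed grade therefore does little. A consistent tilt across a whole group does much more, but nothing in the documents says that a tilt of that size would occur.

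**The case against.** The case against runs as follows.

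- **The scorer is inferred.** The sentence on scoring is in the passive voice. A reader might infer that the plan has the planning team score with the group known. It does not say so. It only leaves this open, and the order of the steps makes it likely. This limit stands.
- **The score is a minor outcome.** The primary objective is dosimetric and the secondary is cosmesis. The score is in neither, nor in the list of dosimetric variables, and its formal test is inferred from the general analysis sentence. A reader might take it as the study's direct test of a closure hypothesis, but that hypothesis is a remark in the background. This stands and lowers the priority.
- **The cited gap does not measure bias.** With groups of 6 or 7, one patient is 14-17% of a group, and it is tempting to set that against the 16-point gap in the cited series. But that share is the same with or without masking, the planned summary is a mean, and the scales differ. The comparison should not be used.
- **The blind is weak.** A visible seroma is both the thing graded and a hint of the technique. Clips, the copper wire and breast shape may also give it away. With 20 scans, the same reader may remember some. This stands. Coding still removes the group label, the operation note and the existing contours, and random order weakens recall. A reader not involved in planning would be stronger but needs another person.

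**Conclusion.** The concern holds in a limited form. A subjective score is summarised by surgical technique, the direction is hypothesised in advance, and no step in the available text keeps the technique from the scorer. Expectation could bias this comparison.

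The size is unknown. On the assumptions above, it ranges from almost nothing for one regraded patient to roughly two to three times the nominal 5% error rate for a half-point tilt under ANOVA, and more for a full point. These figures illustrate sensitivity and do not estimate what would happen.

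A reader might infer that the main results are compromised. The documents do not support that: the dosimetric variables rest on the contour and the plans, and the score does not enter them. The change is worth making because it costs little and leaves treatment alone. The study does not depend on it.

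**What to change.** Add to Material and methods, after the description of the scale:

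- State who assigns the score.
- After accrual ends, export the 20 boost CTs under a study code, without contours, name, operation note or group.
- The existing reader scores them in random order, and this score is the one analysed.
- Clinical contouring and planning stay as written.
- Report as a limitation that the blind is partial, because the seroma, clips, wire or breast shape may suggest the technique and the reader may recall some scans.

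The cost is a little extra work for coded export and one further reading of 20 stored scans. No extra scan or reader is needed. Results for the score come only at the end of the study.

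### The PTV is not limited at the skin or chest wall, so near the skin RCI exceeds 1 for a plan that exactly covers the in-body PTV, and the PTV/breast ratio can count volume that is not breast

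*Combined protocol and SAP*

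**What the plan says.** All references are to the combined protocol and SAP.

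- **CTV** (Material and methods, target volumes): "The CTV will be generated by using a 15 mm uniform expansion from the lumpectomy cavity but limited by skin and chest wall".
- **PTV** (the following sentence): "The CTV will be extended by an additional 10 mm uniform expansion to generate the PTV". No limit is stated, and the document defines no separate PTV for evaluation.
- **Reported variables** (Material and methods, dosimetric variables): besides PTV volume, "the ratio between the PTV volumes to the whole breast volume will be determined". For RCI: "It is the ratio of volume of the PTV to the volume that receives 95% prescribed dose or higher". For DHI: "It is ratio of dose received by 95% of PTV volume to the dose received by 5% of PTV volume". The first normal structure listed is "normal ipsilateral breast tissue (Whole breast volume- PTV volume", with the bracket closing there.
- **Plans**: "Treatment plans for tumor bed boost irradiation will be made using both electrons and photons with 3DCRT technique for each patient".
- **Primary objective** (Aims and Objectives), which these variables serve: "To evaluate dosimetric outcomes in tumor bed boost irradiation in patients undergoing breast conservative surgery using three different surgical techniques".

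**The concern.** A uniform expansion taken literally crosses whatever boundary lies within its reach. Because the limit is written for the CTV and left out one sentence later for the PTV, a planner who follows the text produces a PTV that runs into air at the skin and into chest wall or lung behind the breast.

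Three reported quantities depend on this.

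- **RCI.** Air enters the numerator, but the 95% dose volume lies in tissue. By the plan's formula a value above 1 means that the 95% volume is smaller than the PTV. A plan that covers everything coverable therefore reads as under-covering, by an amount set by cavity depth and size and not by plan quality.
- **DHI.** Its numerator is the dose received by 95% of the PTV. If more than 5% of the PTV is air and the planning system counts that air in the dose-volume data, the numerator can be set by air.
- **PTV/breast ratio.** Its numerator is no longer contained in its denominator, on the skin side or the chest-wall side.

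Seroma volume and doses to lung, heart and contralateral breast are not affected.

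**Working it through.** The plan gives no volume, depth or RCI figure to reproduce. The 25 mm threshold follows from the text. The volumes below are illustrative.

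**Step 1. Reach of the PTV.** Inputs from the plan: CTV margin 15 mm, limited; PTV margin 10 mm, not limited. Let d be the gap from cavity edge to boundary. The PTV passes the boundary by 10 mm if d ≤ 15, by 25 − d mm if 15 < d < 25, and not at all if d ≥ 25. At d = 20 mm it passes by 5 mm.

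**Step 2. Share of the PTV beyond one boundary.** Assumptions not in the documents: a spherical cavity, a flat boundary and a 1 mm voxel grid. The CTV is the cavity plus 15 mm, cropped; the PTV is everything within 10 mm of the CTV.

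| Gap (mm) | radius 10 mm | radius 15 mm | radius 20 mm |
|---|---|---|---|
| 5 | 14.6% | 11.6% | 9.3% |
| 10 | 10.3% | 8.0% | 6.5% |
| 15 | 5.5% | 4.2% | 3.4% |
| 20 | 1.4% | 1.0% | 0.8% |
| 25 | 0% | 0% | 0% |

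The shares move slightly with grid placement. Another 1 mm run gives 11.2, 7.7, 3.7 and 0.8% for radius 15 mm at gaps of 5 to 20 mm.

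**Step 3. RCI when the boundary is skin.** Suppose the 95% volume equals the in-body PTV exactly. Then RCI = V_PTV / (V_PTV − air) = 1 / (1 − air share). For radius 15 mm:

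- gap 5 mm: 1 / (1 − 0.116) = 1.13
- gap 10 mm: 1 / (1 − 0.080) = 1.09
- gap 15 mm: 1 / (1 − 0.042) = 1.04
- gap 20 mm: 1 / (1 − 0.010) = 1.01
- gap 25 mm: 1.00

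When the boundary is the chest wall, the extra volume is tissue and can receive 95% of the dose. A plan fitted to the full PTV then scores 1.00, so no inflation follows from the definition alone.

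**Step 4. Both boundaries.** Central cavity of radius 15 mm in a 50 mm slab (10 mm gap each side): PTV 258.8 cc, of which 21.1 cc is air, 21.1 cc is beyond the chest wall and 216.6 cc is inside the breast. A 0.5 mm grid gives 260.3 cc and 217.6 cc.

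- RCI as written: 258.8 / (258.8 − 21.1) = 258.8 / 237.7 = 1.09.
- PTV/breast ratio at an assumed 600 cc breast: 258.8 / 600 = 0.43, against 216.6 / 600 = 0.36 for the part inside the breast. At 400 cc: 0.65 against 0.54. At 1000 cc: 0.26 against 0.22.
- Normal breast, if read as subtracting two volumes, at 600 cc: 600 − 258.8 = 341 cc, against 600 − 216.6 = 383 cc by structure subtraction.

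Over 12 central cases (radius 10, 15, 20 mm; slab 40, 50, 60, 80 mm), 0 to 26% of the PTV lies outside the breast and RCI as written runs 1.00 to 1.15.

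**Step 5. DHI.** In those 12 cases the air share exceeds 5% in 7. One case (radius 10 mm, 50 mm slab) sits near the threshold, at 5.5% here and 4.9% on another grid, which would make it 6. Whether DHI then changes depends on how the planning system treats dose outside the skin, which is not stated. If air is left out of the dose-volume data, DHI is unaffected.

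**Step 6. Which crop removes the RCI offset.** Again take the 95% volume as the in-body PTV.

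- Numerator cropped at the skin only: 237.7 / 237.7 = 1.00, and 1.00 in all 12 cases.
- Numerator cropped at skin and chest wall: 216.6 / 237.7 = 0.91, and 0.85 to 1.00 over the 12 cases. For an off-centre cavity (radius 15 mm, 60 mm slab, skin gap 25 mm, chest-wall gap 5 mm), RCI as written is 1.00 and this crop gives 1 − 0.116 = 0.88.

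Cropping the numerator at the chest wall therefore only moves the offset from shallow cavities to deep ones.

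**The case against.** The strongest reply is that no planned comparison is shown to be harmed. The electron and photon plans for a patient share one PTV, so it cancels from the ratio of their RCIs. The plan sets no target or acceptance limit for RCI, DHI or the breast ratio. The study is a pilot of twenty patients, and planners may crop the PTV by habit. Nor does the plan call the PTV/breast ratio a share of the breast.

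Much of this stands. The within-patient electron/photon RCI ratio is indeed unaffected. The ratio point is partly one of definition, and the normal-breast point is a wording clarification. The effect is also small near the threshold, about 1% of the PTV at a 20 mm gap.

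It does not remove the point. RCI is to be reported for each plan, and the rule as written yields a value above 1 for a plan that covers all of the PTV inside the body. If planners do crop, the text does not say so, and a reader cannot tell which PTV was used.

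A reader might infer that the surgical groups are compared with bias, because cavity depth could differ by closure technique. The documents give no depths by group, so this is not supported. A reader might also infer that RCI is inflated near the chest wall in the same way. It is not, because that volume is tissue and can be covered. Finally, a DHI of zero does not follow from the plan: it would need air to be counted and reported at zero dose.

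**Conclusion.** The point holds as a defect in the definition of the reporting volume and should be corrected. Under the rule as written, a cavity edge within 25 mm of the skin puts air into the RCI numerator. An edge within 25 mm of skin or chest wall puts non-breast volume into the PTV/breast ratio.

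In the illustrative model the RCI offset is negligible at a gap of 20 mm or more, about 4% at 15 mm, and about 9 to 13% at 10 to 5 mm for a 15 mm radius cavity. These sizes rest on an assumed spherical cavity, flat boundaries, assumed breast volumes and a 95% volume equal to the in-body PTV. The plan gives no cavity depth, cavity size or breast thickness, so the size in this trial and the number of patients affected are unknown. The DHI effect is conditional on the planning system's handling of air. Nothing here shows that the treatment volume is wrong.

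**What to change.** State the following in Material and methods, for reporting only:

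1. Compute RCI and DHI on the PTV cropped at the skin. Keep the 95% volume as the plan defines it, wherever it lies, so that spill into chest wall and lung still lowers RCI. Do not crop the RCI numerator at the chest wall.
2. Compute the PTV/breast ratio from the part of the PTV inside the breast, and obtain normal ipsilateral breast by structure subtraction, not by subtracting two volumes.
3. List the uncropped PTV volume beside the cropped one.
4. Apply this identically to all three groups and to both plans.

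The treatment PTV and fields stay as they are.

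The cost is one or two structure crops per patient and a few sentences of text. Values become less directly comparable with studies that report an uncropped PTV, which item 3 mitigates.

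Two limits should be known. Cropping does not make PTV volume less variable: at radius 15 mm and slabs of 40 to 80 mm, the part inside the breast runs 183 to 265 cc against 241 to 265 cc uncropped. And the skin crop gives RCI 1.00 only for a plan fitted to the in-body PTV. A plan fitted to the 216.6 cc inside the breast would score 237.7 / 216.6 = 1.10, because part of the in-body PTV is then not covered. The plan should therefore also say which volume the plans are fitted to.
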